5.4.1 Replacement policy

Additional patients may be enrolled in the study. If a patient is considered as non-evaluable in Part A or in Part B, enrollment of additional patients to the current treatment group will be considered if there are fewer than the required number of evaluable patients. Minimum numbers of evaluable patients per treatment group in Part A are defined in the guidelines for cohort progression and determination section ([Section 6.5](#)). Minimum numbers per treatment group in Part B are defined in the Cohort Specific Information outlined in [Section 12](#).

Replacements of patients will be done on a case-by-case basis.

5.4.2 Participant numbering

Each patient is identified in the study by a Participant Number (Participant No.), that is assigned when the patient is enrolled for screening and is retained for the patient throughout his/her participation in the trial. A new Participant No. will be assigned at every subsequent enrollment if the patient is rescreened. The Participant No. consists of the Site Number (Site No.) (as assigned by Novartis to the investigative site) with a sequential participant number suffixed to it, so that each patient's participation is numbered uniquely across the entire database. Upon signing the informed consent form, the patient is assigned to the next sequential Participant No. available.

A new ICF will need to be signed if the investigator chooses to rescreen the patient after a patient has screen failed, and the patient will be assigned a new Participant No.

6 Study treatment(s) and concomitant therapy

6.1 Study treatment(s)

The investigational compounds being evaluated in this study will be administered orally. Refer to compound-specific information in [Section 12](#).

6.1.1 Additional study treatments

No other treatment beyond investigational drugs and control drugs are included in this trial.

6.1.2 Treatment arms/group

In Part A, patients will be randomized at the screening visit to receive a single dose of an anti-malarial agent at one of the dose levels at equal ratios.

In Part B, patients will be randomized at the screening visit to receive a single dose of a combination of anti-malarial agents or the standard of care (Coartem).

See [Section 12](#) for cohort specific information.

6.1.3 Treatment duration

For Part A, the planned duration of treatment is 1 day.

For Part B, the planned duration of treatment is 1 day for patients randomized to the active investigational medicinal products administered as a loose combination or 3 days for patients randomized to the standard of care arm. Patients may be discontinued from SoC treatment earlier at the discretion of the investigator or the patient.

6.2 Preparation, handling, storage, and accountability

Each study site will be supplied with study treatment(s) in packaging as described under the Investigational and control drugs in [Section 12](#).

A unique medication number is printed on the study medication label.

Investigator staff will identify the study medication kits to dispense to the patient by contacting the IRT and obtaining the medication number(s). The study medication provided by Novartis has a 2-part label (base plus tear-off label), immediately before dispensing the medication kit to the patient, site personnel will detach the outer part of the label from the packaging and affix it to the source document.

6.2.1 Handling of study treatment

Study treatment must be received by a designated person at the study site, handled and stored safely and properly and kept in a secured location to which only the investigator and designated site personnel have access. Upon receipt, all study treatment must be stored according to the instructions specified on the labels.

Clinical supplies are to be dispensed only in accordance with the protocol. Technical complaints are to be reported to the respective Novartis Clinical Outcome Assessment Quality Assurance.

Medication labels will be in the local language and comply with the legal requirements of each country. They will include storage conditions for the study treatment but no information about the patient except for the medication number.

The investigator or designated site staff must maintain an accurate record of the shipment and dispensing of study treatment in a drug accountability log. Monitoring of drug accountability will be performed by field monitors during site or remote monitoring visits, and at the completion of the trial. The investigator must provide accountability also for locally sourced materials used for administration as applicable.

The site may destroy and document destruction of unused study treatment, drug labels and packaging, as appropriate in compliance with site processes, monitoring processes, and per local regulation/guidelines. Otherwise, the investigator will return all unused study treatment, packaging, drug labels, and a copy of the completed drug accountability log to the Novartis monitor or to the Novartis address provided in the Investigator folder at each site.

6.2.2 Handling of other treatment

The following non-study treatment has to be monitored specifically:

- Coartem or other local standard anti-malarial agent per investigator discretion may be administered as rescue medication in case of treatment failure. Monitoring of rescue medication compliance and drug accountability will be performed by the field monitors during site or remote monitoring visits, and at the completion of the trial.

6.2.3 Instruction for prescribing and taking study treatment

Refer to [Section 12](#) for compound specific instructions for prescribing and taking study treatment.

All kits of study treatment assigned by the IRT will be recorded in the IRT system.

6.3 Measures to minimize bias: randomization and blinding

6.3.1 Treatment assignment, randomization

At the screening visit after patient eligibility is confirmed, all eligible patients will be randomized via Interactive Response Technology (IRT) to one of the treatment arms. The investigator or his/her delegate will contact the IRT after confirming that the patient fulfills all the inclusion/exclusion criteria. The IRT will assign a randomization number to the patient, which will be used to link the patient to a treatment arm and will specify a unique medication number for the first package of study treatment to be dispensed to the patient.

The randomization numbers will be generated using the following procedure to ensure that treatment assignment is unbiased and concealed from patients and investigator staff. A patient randomization list will be produced by the IRT provider using a validated system that automates the random assignment of participant numbers to randomization numbers. These randomization numbers are linked to the different treatment arms, which in turn are linked to medication

numbers. A separate medication list will be produced by or under the responsibility of Novartis Global Clinical Supply (GCS) using a validated system that automates the random assignment of medication numbers to packs containing the study treatment.

The randomization scheme for patients will be reviewed and approved by a member of the Randomization Office or by a designated member following CRO procedures.

6.3.2 Treatment blinding

In Parts A and B of the study, treatment will be open to patients, investigator staff, persons performing the assessments and the Novartis clinical trial team (CTT). Because the primary endpoint is an objective endpoint for Part A, blinding is not necessary except for the site microscopists who will be blinded. As the dosing regimens are different (i.e., CCI vs. 3 day BID dosing for Coartem) for Part B, it would be impractical to blind the study, hence it will be unblinded except for the site microscopists who will be blinded. In addition, food requirements could be different for Coartem and investigational drug and thus preventing the blinding.

The study statistician, statistical programmer, data analyst (e.g., biomarker, PK) will be able to access the full randomization list from the start of the study and are allowed to share unblinded information with the rest of the clinical team as appropriate for internal decision making. For example, unblinded summaries and unblinded individual data can be shared with the team whenever necessary.

At the time of safety review/interim analysis for efficacy, the Sponsor will create and review unblinded interim reports. These summaries/reports will be shared with the DMC for review and trial recommendations. More details will be provided in the DMC charter.

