LLN	lower limit of normal
LLOQ	lower limit of quantification
LPF	Late Parasitological Failure
CCI	
MDMA	3,4-Methylenedioxy-N-methylamphetamin
MedDRA	Medical dictionary for regulatory activities
mg	milligram(s)
mL	milliliter(s)
MoA	Mechanism of action
MPC	minimum parasitocidal concentration
MRI	Magnetic resonance imaging
MS	mass spectrometry
NOAEL	No Observed Adverse Effect Level
NSAIDs	Non-steroidal anti-inflammatory drugs

p.o.	Oral(ly)
PC	Parasite Clearance
CCI	
PCP	Phenyl-cyclohexyl-piperidin
PCR	Polymerase Chain Reaction
PCT	Parasite Clearance Time
PCV	Packed cell volume (hematocrit)
PD	Pharmacodynamic(s)
PK	Pharmacokinetic(s)
PPS	Per-protocol Set
CCI	
PT	prothrombin time
CCI	
qRT-PCR	quantitative reverse-transcription polymerase chain reaction
QTcF	QT interval corrected by Fridericia's formula
RAS	Randomized Analysis Set
RBC	Red Blood Cell
RNA	Ribonucleic acid
SAE	Serious Adverse Event
SAF	Safety Analysis Set
SAP	Statistical Analysis Plan
SBP	Systolic Blood Pressure
SCID	severe combined immunodeficiency
sCr	Serum creatinine
SD	standard deviation
SGOT	Serum Glutamic Oxaloacetic Transaminase
SGPT	Serum Glutamic Pyruvic Transaminase
SmPC	Summary of Product Characteristics
SMQ	Standardized MedDRA Query
SoC	Standard of Care
SUSAR	Suspected Unexpected Serious Adverse Reaction
ULN	upper limit of normal
WBC	White Blood Cells
WHO	World Health Organization
WWARN	World Wide Antimalarial Resistance Network

Definitions

Additional treatment	Medicinal products that may be used during the clinical trial as described in the protocol, but not as an investigational medicinal product (e.g., any background therapy)
Assessment	A procedure used to generate data required by the study
Biologic Samples	A biological specimen including, for example, blood (plasma, serum), saliva, tissue, urine, stool, etc. taken from a study participant
Clinical Outcome Assessment (COA)	A measure that describes or reflects how a participant feels, functions, or survives
Clinical Trial Team	A group of people responsible for the planning, execution and reporting of all clinical trial activities. Examples of team members include the Study Lead, Medical Monitor, Trial Statistician etc.
Coded Data	Personal Data which has been de-identified by the investigative center team by replacing personal identifiers with a code.
Cohort	A group of individuals who share a common exposure, experience or characteristic, or a group of individuals followed-up or traced over time

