6.8 Concomitant and other therapy

6.8.1 Concomitant therapy

All medications, procedures, and significant non-drug therapies (including physical therapy and blood transfusions) administered after the patient was enrolled into the study must be recorded on the appropriate Case Report Forms.

Concomitant medication is defined as any medication, other than the study treatments being evaluated in this study, which is given at least once between the day of first dose of randomized study medication and the last day of study visit (including those which were started pre-baseline

and continued into the treatment period), including prescription and over-the-counter medicines, and any traditional or herbal remedies.

Paracetamol (daily total dose not to exceed 3g) as an antipyretic and metopimazine (or if not available, any other antiemetic which is not known to prolong QT and/or cause Torsades de Pointes) for repeated vomiting are recommended. If paracetamol or equivalent drug is given as an antipyretic up to 72 hours prior first dose, it must be reported as prior medication.

The investigator must instruct the patient to notify the study site about any new medications he/she takes after the patient was enrolled into the study. All medications, procedures and significant non-drug therapies (including herbal therapy, physical therapy and blood transfusions) administered after the patient was enrolled into the study must be recorded in the concomitant medications eCRF.

Each concomitant drug must be individually assessed against all exclusion criteria/prohibited medication. If in doubt, the investigator should contact the Novartis medical monitor before randomizing a patient or allowing a new medication to be started. If the patient is already enrolled, contact Novartis to determine if the patient should continue participation in the study.

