8.4.4 Clinical safety laboratory tests

As per [Section 4.6](#), during a public health emergency as declared by local or regional authorities' i.e., pandemic, epidemic or natural disaster, that limits or prevents on-site study visits, if patients cannot visit the site for protocol-specified safety lab assessments, an alternative lab (local) collection site may be used.

Clinically significant abnormalities must be recorded as either medical history/current medical conditions or adverse events as appropriate.

In the case where a laboratory range is not specified by the protocol, but a value is outside the reference range for the laboratory at screening, a decision regarding whether the result is of clinical significance or not shall be made by the investigator (in consultation with the Sponsor) and shall be based, in part, upon the nature and degree of the observed abnormality. The assessment may be repeated once prior to randomization.

All abnormal lab results must be evaluated for criteria defining the inclusion/exclusion criteria, an adverse event and reported as such if the criteria are met. For those lab adverse events, repeated evaluations are mandatory until normalization of the result(s) or until the result is no longer considered to be clinically significant.

In all cases, the investigator must document in the source documents, the clinical considerations (i.e., result was/was not clinically significant and/or medically relevant) in allowing or disallowing the patient to continue in the study.

Local laboratories will be used for analysis of safety specimens.

Urinalysis

A midstream urine sample (approx. 30 mL) will be obtained, in order to avoid contamination with epithelial cells and sediments, and allow proper assessments.

Special clinical laboratory evaluations

All abnormal lab results must be evaluated for criteria defining an adverse event and reported as such if the criteria are met. For those lab adverse events, repeated evaluations are mandatory until normalization of the result(s) or until the result is no longer considered to be clinically significant.

Table 8-2 Laboratory assessments

The CCI logo is displayed in red text on a black rectangular background.

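### Statistics staff may hold the full randomisation list, including unreleased allocations, from study start, and nothing keeps those allocations from sponsor staff who are consulted on eligibility

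*Protocol*

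**What the plan says.** Protocol 6.3.2 makes the study open-label: "treatment will be open to patients, investigator staff, persons performing the assessments and the Novartis clinical trial team (CTT"). Only the site microscopists are blinded. The section then says that the statistician, programmer and data analyst "will be able to access the full randomization list from the start of the study and are allowed to share unblinded information". The recipients are their colleagues on the clinical team, and the sharing is meant to serve internal decisions. Its example is that "unblinded summaries and unblinded individual data can be shared with the team whenever necessary".

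Protocol 6.3.1 has the IRT provider produce the list. The site confirms eligibility and then contacts the IRT, which returns the assignment. The stated aim of the procedure is to "ensure that treatment assignment is unbiased and concealed from patients and investigator staff".

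Two other sections bring the sponsor in before randomisation. Under 6.8.1, if there is doubt about a concomitant drug, "the investigator should contact the Novartis medical monitor before randomizing a patient or allowing a new medication to be started". Under 8.4.4, when a screening laboratory value is outside the reference range and the protocol sets no limit for it, the decision on clinical significance "shall be made by the investigator (in consultation with the Sponsor").

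The protocol's Definitions list describes the clinical trial team as follows: "Examples of team members include the Study Lead, Medical Monitor, Trial Statistician etc".

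**The concern.** Blinding and allocation concealment protect against different things. Open-label conduct means that treatments already assigned are known. Concealment means that nobody with a say in whether a patient enters knows what the next assignment will be. A study can give up the first and keep the second, and Table 4-1 gives reduction of selection bias as a reason for randomising.

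The access rule in 6.3.2 is not limited to assignments already made. If an unreleased allocation reached someone advising on a borderline patient, that advice could, even unintentionally, depend on the arm the patient would enter. The arms could then differ in prognosis at baseline. This matters most in Part B, where the primary analysis compares the combination with standard of care for non-inferiority on PCR-corrected ACPR. Neither objective endpoints nor blinded microscopists can correct a difference in who was enrolled.

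**Working it through.** No formula applies, since the point rests on no figure in the plan. The check is whether the visible text links the list to eligibility advice, and whether anything breaks that link.

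1. **Does the access include future allocations?** Yes. Section 6.3.2 refers to the full list and to the start of the study. At that time no patient has been randomised, so every entry is an unreleased allocation.

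2. **May information move from the statistics staff to the wider team?** Yes, for unblinded information in general. The examples are summaries and individual data. The list is neither named nor excluded.

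3. **Is the medical monitor in that team?** Yes. The Definitions list names the medical monitor and the trial statistician as members of the same team.

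4. **Does the medical monitor, or the sponsor, advise before randomisation?** Yes, in two limited situations: a doubtful concomitant drug (6.8.1) and a screening laboratory value outside the reference range with no protocol limit (8.4.4).

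5. **Does the concealment statement cover these people?** No. Section 6.3.1 names patients and investigator staff and does not mention the sponsor.

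6. **Does another visible passage close the gap?** None was found. Section 6.3.1 says who produces the list and who approves the scheme, but not who is kept from seeing it. Table 4-1 defends the open-label design by the objectivity of the endpoints and the blinding of microscopists. Both concern biased assessment, not biased entry. The visible SAP text does not address access to the list.

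7. **Does any planned activity need future allocations?** None that is visible. The data reviews in 4.4, including the look at about six patients per arm in Part B, and the interim reports for the DMC all use patients already enrolled. Section 10.1.5.2 has the IRT vendor track randomisation codes and send data to the sponsor at set times, so assignments already made can be supplied by that route.

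Steps 1, 3, 4 and 5 are explicit in the text. That unreleased allocations could reach the medical monitor follows from step 2 only because nothing forbids it.

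**Size.** Block size, stratification, the number of sponsor consultations and the prognosis of borderline patients are not given. No estimate of bias can be derived.

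**The case against.** The strongest reply is that the people who enrol patients remain concealed. Nothing in 6.3.2 gives sites the list, so 6.3.1 and 6.3.2 do not contradict each other. The site confirms eligibility itself, and under 8.4.4 the laboratory decision is the investigator's. Consultation is confined to doubtful drugs and some laboratory values. The sharing clause is tied to internal decisions, and individual data exist only for patients already enrolled. Holding a list is also not the same as knowing which entry comes next in a multi-centre study randomised through an IRT. Bias would need several steps together: disclosure of unreleased codes, knowledge of the current position in the list, a borderline patient, and advice influenced by what was known.

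All of this stands, and it makes bias less likely. It does not remove the gap, because each step is left to good practice and none is ruled out by the protocol.

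Two stronger readings are tempting and unsupported. A reader might infer that the list is to be shared with the clinical team, or that concealment is already broken. The text permits sharing unblinded information and gives summaries and individual data as examples; it does not say that the list is passed on. A reader might also use the 30 patients per arm in SAP Table 3-5 to turn a supposed number of steered patients into percentage points of cure rate. The documents give no such number and no prognosis for such patients, so the result would only restate the assumption.

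**Conclusion.** The point holds in a limited form. Statistics staff have express access to unreleased allocations from study start. They may share unblinded information with a team that includes the medical monitor, and no visible rule keeps unreleased allocations from the sponsor staff who may be consulted on eligibility. The open-label design explains access to assignments already made and gives no reason for access to the rest.

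This is a gap in a stated safeguard, not evidence that bias has occurred or was intended. Its size is unknown.

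The conclusion assumes that the redacted passages and the documents not supplied, such as the DMC charter and the randomisation procedures mentioned in 6.3.1, contain no restriction on access. It also assumes that the text is current. The latest amendment listed in the supplied protocol is Amendment 2 of June 2023, whereas the SAP introduction says it is based on protocol version 03 of 20 March 2024.

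**What to change.** First check whether protocol version 03 keeps the access wording in 6.3.2. If it does, make two changes:

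- **Section 6.3.2:** limit access by the statistician, programmer and data analyst, and any sharing with the clinical team, to the assignments of patients already randomised. State that unreleased allocations stay with the IRT provider or the Randomization Office until enrolment in the cohort closes.
- **Section 6.3.1:** extend the concealment statement to sponsor staff who advise on eligibility, including the medical monitor and those consulted on screening laboratory values.

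The cost is a wording change and an IRT access setting. On the visible text no planned data review, interim report or DMC package is lost, because each concerns patients already randomised. If an existing procedure already restricts access in this way, a sentence in 6.3.2 referring to it would be enough for the first change.

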6.4 Study treatment compliance

In this study, the patients will be dosed at the investigator's center by qualified members of the site staff. Details of each dose of study drug will be recorded in the CRF.

Pharmacokinetic parameters (measures of treatment exposure) will be determined in all patients treated with all anti-malarial agents, as detailed in the Cohort Specific Information section ([Section 12](#)).

